19. TOPLINE AND FINAL DATABASE TRANSFER

After database lock, the topline results that contains only five tables will be delivered to the study sponsor before the complete set of outputs. The topline tables will include:

- 1) Table 14.1.1.1 Subject Disposition
- 2) Table 14.2.2.2.1 Change from Baseline in WOMAC Pain Score by Visit
- 3) Table 14.2.2.2.2 Change from Baseline in WOMAC Physical Function Score by Visit
- 4) Table 14.2.2.2.3 Change from Baseline in WOMAC Stiffness Score by Visit
- 5) Table 14.3.1.2 Summary of Treatment-Emergent Adverse Events by System Organ Class and Preferred Term

After finalization of the analysis and database lock, the following will be transferred to the study sponsor:

- Randomization List
- Statistical Analysis Plan
- Annotated CRF
- All SAS programs used in the project for statistical analysis, report tables generation, and analysis dataset creation (including all source code for any macros that may be used)
- Tables, listings, and figures as included in the clinical study report
- Final SAS datasets, with full audit trail from initial data entry through final accepted version
- ADaM datasets that are necessary for analysis will be programmed in addition to SDTM
(to be modeled in accordance with the Analysis Data Model version 2.1: Implementation Guide version 1.1, and the CDISC Study Data Tabulation Model version 1.4 or latest: Implementation Guide version 3.2 or latest)
- Define.xml for ADaM and SDTM data sets (to be modeled in accordance with the CDISC Define-XML Specification Version 2.0 or latest)
- Study data and analysis data reviewer guides (to be modeled in accordance with the Analysis Data Reviewer's Guide Completion Guidelines Version 1.1, and the Study Data
- Reviewer's Guide Completion Guidelines Version 1.2) for any unavoidable CDISC checker errors or warnings (found using Pinnacle21)
- Pinnacle21 reports with explanation for errors/warnings if any
- Relevant Correspondence

Noven Pharmaceuticals, Inc.

Protocol HP-5000-US-07

Statistical Analysis Plan

Page 48 of 58

Database archiving at [REDACTED] is performed in accordance with [REDACTED] SOPs, which ensure security, integrity, disaster recovery, and adequate backup.

Noven Pharmaceuticals, Inc.
Protocol HP-5000-US-07

REFERENCES

1. PERMUTT T. SENSITIVITY ANALYSIS FOR MISSING DATA IN REGULATORY SUBMISSIONS. *STAT MED*. 2016;35(17):2876–2879

APPENDIX 1. PARTIAL DATE CONVENTIONS

Imputed dates will NOT be presented in the listings. The below tables in Appendix 1 represents the study medication start date as patch application and study medication end date as patch removal.

ALGORITHM FOR TREATMENT EMERGENCE OF ADVERSE EVENTS

START DATE	STOP DATE	ACTION
Known	Known	If start date < study medication start date or start date>study medication end date + 1 day, then not TEAE If study medication start date ≤ start date ≤ study medication end date + 1 day, then TEAE
	Partial	Impute stop date as latest possible date (i.e. last day of month if day unknown or 31st December if day and month are unknown), then: If start date < study med start date or start date>study med end date + 1 day, then not TEAE If study med start date ≤ start date ≤ study med end date + 1 day, then TEAE
	Missing	If start date < study med start date or start date>study med end date + 1 day, then not TEAE If study med start date ≤ start date ≤ study med end date + 1 day, then TEAE
Partial, but known components show that it cannot be on or after study medication start date or cannot be	Known	Not TEAE

Noven Pharmaceuticals, Inc.

Protocol HP-5000-US-07

Statistical Analysis Plan

Page 51 of 58

START DATE	STOP DATE	ACTION
before study medication end date		
	Partial	Not TEAE
	Missing	Not TEAE
Partial, could be on or after study medication start date but before study med end date	Known	If stop date < study med start date, then not TEAE If stop date \geq study med start date, then TEAE
	Partial	Impute stop date as latest possible date (i.e. last day of month if day unknown or 31st December if day and month are unknown), then: If stop date < study med start date, then not TEAE If stop date \geq study med start date, then TEAE
	Missing	Assumed TEAE
Missing	Known	If stop date < study med start date, then not TEAE If stop date \geq study med start date, then TEAE
	Partial	Impute stop date as latest possible date (i.e. last day of month if day unknown or 31st December if day and month are unknown), then: If stop date < study med start date, then not TEAE If stop date \geq study med start date, then TEAE

Noven Pharmaceuticals, Inc.

Protocol HP-5000-US-07

Statistical Analysis Plan

Page 52 of 58

START DATE	STOP DATE	ACTION
	Missing	Assumed TEAE

ALGORITHM FOR PRIOR / CONCOMITANT MEDICATIONS, SURGERIES, PROCEDURES, AND THERAPIES

START DATE	STOP DATE	ACTION
Known	Known	
If stop date < study med start date, assign as prior
 
If stop date \geq study med start date and start date < study med start date, assign as prior concomitant
 
If stop date \geq study med start date and start date \leq end of treatment, assign as concomitant
 
If stop date \geq study med start date and start date > end of treatment, assign as post study

	Partial	
Impute stop date as latest possible date (i.e. last day of month if day unknown or 31st December if day and month are unknown), then:
 
If stop date < study med start date, assign as prior
 
If stop date \geq study med start date and start date < study med start date, assign as prior concomitant
 
If stop date \geq study med start date and start date \leq end of treatment, assign as concomitant
 
If stop date \geq study med start date and start date > end of treatment, assign as post study

	Missing	
If stop date is missing could never be assumed a prior medication
 
If start date \leq end of treatment, assign as concomitant
 
If start date > end of treatment, assign as post treatment

[REDACTED]

[figure not shown]
Noven Pharmaceuticals, Inc.

Protocol HP-5000-US-07

Statistical Analysis Plan

Page 53 of 58

START DATE	STOP DATE	ACTION
Partial	Known	
Impute start date as earliest possible date (i.e. first day of month if day unknown or 1st January if day and month are unknown), then:
 
If stop date < study med start date, assign as prior
 
If stop date \geq study med start date and start date < study med start date, assign as prior concomitant
 
If stop date \geq study med start date and start date \leq end of treatment, assign as concomitant
 
If stop date \geq study med start date and start date $>$ end of treatment, assign as post study

	Partial	
Impute start date as earliest possible date (i.e. first day of month if day unknown or 1st January if day and month are unknown) and impute stop date as latest possible date (i.e. last day of month if day unknown or 31st December if day and month are unknown), then:
 
If stop date < study med start date, assign as prior
 
If stop date \geq study med start date and start date < study med start date, assign as prior concomitant
 
If stop date \geq study med start date and start date \leq end of treatment, assign as concomitant
 
If stop date \geq study med start date and start date $>$ end of treatment, assign as post study

	Missing	
Impute start date as earliest possible date (i.e. first day of month if day unknown or 1st January if day and month are unknown), then:
 
If stop date is missing could never be assumed a prior medication
 
If start date \leq end of treatment, assign as concomitant
 
If start date $>$ end of treatment, assign as post treatment

Missing	Known	
If stop date < study med start date, assign as prior
 
If stop date \geq study med start date, assign as concomitant
 
Cannot be assigned as 'post treatment'

Noven Pharmaceuticals, Inc.

Protocol HP-5000-US-07

Statistical Analysis Plan

Page 54 of 58

START DATE	STOP DATE	ACTION
	Partial	
Impute stop date as latest possible date (i.e. last day of month if day unknown or 31st December if day and month are unknown), then:
 
If stop date < study med start date, assign as prior
 
If stop date \geq study med start date, assign as concomitant
 
Cannot be assigned as 'post treatment'

	Missing	Assign as concomitant

Noven Pharmaceuticals, Inc.

Protocol HP-5000-US-07

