##### **13.4.4.1 Adverse Events**

All AEs will be coded using the latest version of the Medical Dictionary for Regulatory Activities (MedDRA).

Treatment-emergent AEs are defined as:

- AEs with onset at the time of or following the start of treatment with study drug through the Follow-up Visit or Early Termination Visit, whichever occurs first. The number and percentage of subjects with AEs will be displayed for each treatment group by system organ class and preferred term. Summaries of AEs by severity and relationship to study drug will also be provided. Serious adverse events and AEs resulting in discontinuation of study drug will be summarized separately in a similar manner. Subject listings of AEs, SAEs, and AEs causing discontinuation of study drug will be produced.

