3.3 CHANGES TO ANALYSIS FROM PROTOCOL

Not Applicable

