18.1 ADVERSE EVENTS

AEs will be coded using MedDRA version in effect at the time of final database lock.

TEAEs are defined as:

AEs that begin or pre-existing conditions that worsen at the time of or following the start of treatment with study drug through the Follow-up Visit or Early Termination Visit, whichever occurs first.

See [Appendix 2](#) for handling of partial or completely missing dates for AEs. In the case where it is not possible to define an AE as treatment emergent or not, the AE will be classified as the worst case, i.e., treatment emergent. Adverse event listings will display start and end dates as collected (even if partial) and they will be sorted by treatment group, subject ID, then by SOC/PT in alphabetical order.

The AE summaries that will be provided are described below in sub-sections [18.1.1](#) and [18.1.2](#). Additional details are included in the relevant table and listing shells.

Listings will include all adverse events.

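### The SAP gives two end points for the treatment-emergent window, so the same fully dated adverse event can be flagged either way

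*SAP*

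**What the plan says.** SAP 18.1 defines TEAEs as events that begin, or pre-existing conditions that worsen, at or "following the start of treatment with study drug through the Follow-up Visit or Early Termination Visit, whichever occurs first". Protocol 13.4.4.1 sets the same end, "through the Follow-up Visit or Early Termination Visit, whichever occurs first". SAP 3.3, the place to declare departures from the protocol, reads "Not Applicable".

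The algorithm in SAP Appendix 1 uses a different end. Its rows for a known start date (stop date known, partial or missing) all carry the rule that the first row words as "start date>study medication end date + 1 day, then not TEAE". The appendix equates the medication end date with patch removal.

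SAP 18.1 invokes an appendix only "for handling of partial or completely missing dates for AEs". The one it names is Appendix 2, which holds SAS code; the date algorithm is in Appendix 1. Where status cannot be determined, 18.1 says "the AE will be classified as the worst case, i.e., treatment emergent". SAP 18.1.1 adds a separate summary of events in follow-up after the last patch removal.

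**The concern.** The two rules disagree for events with complete dates, where nothing needs imputing. A programmer who follows 18.1 and one who follows the Appendix 1 table will produce different flags from the same data, and neither would be misreading the SAP.

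TEAE incidence is a named safety endpoint (SAP 2.3). The flag feeds the system organ class and preferred term table (14.3.1.2), one of the five topline tables in SAP 19, and also the severity, relationship and application-site tables. If Appendix 1 is coded, those tables depart from the protocol definition without a declaration. If the choice is made after unblinding, the safety window is chosen with results in view.

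**Working it through.** The documents give no figure to reproduce. The check is to write both rules as date tests and count the onset days on which they differ.

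**Inputs**
- Patch removal day, R. Completers have the patch removed at Visit 8, nominally Day 84 (protocol 10.1.3 and 10.2).
- Close-out visit day, C. The follow-up call is about 7 days after Visit 8, nominally Day 91 (protocol 10.1.4 and 10.2).
- Protocol 8.2.3 (version 2.0) strongly encourages subjects who stop treatment to remain to the Week 13 call.
- At an Early Termination Visit the patch is removed at that visit (protocol 10.1.5).
- Assumption: the follow-up window is ±2 days, timed from Visit 8. The window row of the schedule table is broken in the available text, so this is a reading of it.

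**Rules**, for onset on or after first dose
- SAP 18.1: TEAE if onset ≤ C.
- Appendix 1: TEAE if onset ≤ R + 1.
- Disputed days = C − (R + 1). A negative value means Appendix 1 is the wider rule.

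| Case | R | C | C − (R + 1) |
|---|---|---|---|
| Completer, call at 7 days | 84 | 91 | 6 (Days 86–91) |
| Completer, call at 5 days | 84 | 89 | 4 |
| Completer, call at 9 days | 84 | 93 | 8 |
| Stops on Day 56, stays to Day 91 | 56 | 91 | 34 |
| Stops on Day 28, stays to Day 91 | 28 | 91 | 62 (Days 30–91) |
| Stops on Day 7, stays to Day 91 | 7 | 91 | 83 |
| Removal Day 40, Early Termination Visit Day 45 | 40 | 45 | 4 |
| Removal at Early Termination Visit, Day 40 | 40 | 40 | −1 (Day 41 is a TEAE under Appendix 1 only) |

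The early-stop and early-termination days are illustrations. The documents give no frequency for such subjects.

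**Partial start dates (a smaller point).** The Appendix 1 rows for partial starts use a third boundary: the event must possibly start before the medication end date. With only the month known, let F be its first day.
- Partial-start row: F < R.
- The + 1 day bound: F ≤ R + 1. This differs from the row when R is F − 1 or F, which is 2 removal dates per month (24 of 365).
- The 18.1 window with a 7-day follow-up: F ≤ R + 7. This differs from the row when R runs from F − 7 to F, which is 8 removal dates per month (96 of 365).

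Protocol 11.2.3 requires a start date and time, so such cases should be uncommon.

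**The case against.** The best defence is that Appendix 1 is not meant for complete dates. Its title is "APPENDIX 1. PARTIAL DATE CONVENTIONS", and 18.1 calls on an appendix only for partial or missing dates. On that reading 18.1 governs known dates. This is a fair reason to prefer 18.1, but it does not remove the conflict: the first row of the algorithm is for known start and known stop dates, and no text says 18.1 overrides it.

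The opposite reading also has support. SAP 6.2 places post-study adverse events from the last patch removal, and 18.1.1 tabulates events after removal separately. An on-treatment convention may have been intended, with 18.1 carrying over the protocol wording. Neither section defines treatment emergence, and the documents do not settle the intent.

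The impact is limited, and that stands. "Listings will include all adverse events"; post-removal events get their own table; the SAE summary (18.1.3) and the death listing (18.1.4) are not worded as restricted to TEAEs; and SAP 18 plans no formal inference on safety unless otherwise noted. The same rule would apply to both arms. The SAP text does not say whether post-removal events are also counted in the TEAE tables. The table shells mentioned in SAP 8 and 18.1 are not in the available documents and might say. The wrong appendix number in 18.1 is a slip and carries no weight by itself.

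**Conclusion.** The concern holds. SAP 18.1 and the protocol set one end to the TEAE window, the known-start rows of Appendix 1 set another, and SAP 3.3 declares no change.

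The figure closest to the documents is 6 disputed onset days for a completer with a call at 7 days, or 4 to 8 under the assumed ±2-day window. For subjects who stop patches early and stay in the study it can be several weeks, and for removal at the Early Termination Visit the difference reverses by one day. These are days, not events: the effect on counts, or on either arm, cannot be computed from the documents. No efficacy conclusion is touched. The point should be settled before unblinding because it affects a topline safety table and its agreement with the protocol.

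**What to change.** 1. In the known-start rows of Appendix 1, replace the + 1 day bound with the end boundary of protocol 13.4.4.1. Alternatively, keep another boundary, record it in SAP 3.3 as a change from the protocol, and amend 18.1 to match.
2. Use the same boundary in the partial-start rows, so that a partial start that could fall inside the window is a TEAE under the worst-case rule of 18.1. Leave the missing-start rows as they are.
3. State in 18.1.1 whether events after the last patch removal are also counted in the TEAE tables, and check that the post-study wording in 6.2 agrees.
4. Correct the reference in 18.1 from Appendix 2 to Appendix 1.

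The cost is SAP wording and one derivation. No new data are needed, since protocol 11.2 already collects adverse events through the Follow-up or Early Termination Visit. Some events may change TEAE status.

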APPENDIX 2. SAS CODE

PROC MIXED:

```
ODS OUTPUT LSMEANS=LSEST DIFFS=LSDIFF COVPARMS=COVS;
PROC MIXED DATA = TEST COVTEST;
CLASS TREATMENT VISIT SUBJECT;
MODEL change in womac pain score = treatment visit treatment*visit baseline womac pain
score;
LSMEANS TRTPN*AVISITN / DIFF CL;
REPEATED VISIT / TYPE = UN SUBJECT = SUBJECT;
RUN;
```

PROC LOGISTIC:

```
proc logistic data="Test" descending;
where visit variable = a given number (e.g., 4)
class treatment / param=ref ;
model respond = treatment PGA baseline value;
run;
```

[REDACTED]

Noven Pharmaceuticals, Inc.

Protocol HP-5000-US-07

[REDACTED]

Statistical Analysis Plan

Page 56 of 58

APPENDIX 3. IMPLEMENTATION OF SENSITIVITY ANALYSES AND ANALYSES FOR OTHER RELEVANT ESTIMANDS

Sensitivity analyses of the primary and key secondary efficacy endpoint will be performed to assess the impact of assumptions about missing data patterns on the primary inferences during the trial.

The change from baseline to Week 12 summary statistics will be presented for both imputation approaches described below. The dropout reason, shift value, treatment group, LS Mean difference values along with 95% CIs will be presented. Nominal p-values comparing the HP-5000 treatment group versus placebo will also be displayed.

a. Multiple Imputation: Pattern Mixture Model (PMM)

Step 0: Missing data will be imputed using a multiple imputation technique assuming MAR for all treatment groups.

Step 1: A shift ($\Delta 1$) will be added to all imputed data in Step 0 in the Placebo group to worsen imputed scores. The range of values $\Delta 1$ can be calculated from $\Delta 1=k1 \times$ the upper bound (UB1) where $k1=0, 0.33, 0.67$, and $1 \times$ the UB1 for $\Delta 1$. The UB1 will be based on the end point, UB1 for WOMAC Pain is 4, UB1 for WOMAC Physical Functioning is 12, and UB1 for WOMAC Stiffness is 2. The UB1's for $\Delta 1$ are selected to be reasonably higher than the SD estimated from the blinded data to provide a sufficiently wide range for the imputation. Note for WOMAC Pain $\Delta 1=0, 1.3333, 2.6667, 4$ for imputation purpose. For WOMAC Physical Functioning $\Delta 1=0, 4, 8, 12$. For WOMAC Stiffness $\Delta 1=0, .6667, 1.3333, 2$.

Step 2: A shift ($\Delta 2$) where $\Delta 2=\Delta 1+ k2 \times$ LS mean difference (LSMD) is also added to the imputed data in Step 0 in the active treatment group to worsen their imputed scores. For each value of $\Delta 1$, the value of $\Delta 2$ will be calculated using $k2 (k2=0, 0.2, 0.4, 0.6, 0.8 \text{ and } 1) \times$ LSMD between the active treatment group vs placebo based on the MMRM primary analysis. It is important to note that if $k2=0$, then $\Delta 2=\Delta 1$, and if $k2=1$, then $\Delta 2=\Delta 1+ LSMD$; therefore, the considered range for $\Delta 2$ is from $\Delta 1$ to $\Delta 1+ LSMD$. A total of 24 combinations of shifts will be added to the imputed values.

Step 3: The primary MMRM model is then applied to each of the complete datasets created from Step 0 through Step 2.

Step 4: Step 0 through Step 3 are then repeated $m=100$ times and PROC MIANALYZE is then applied to combine the estimates using Rubin's combination rules.

Noven Pharmaceuticals, Inc.

Protocol HP-5000-US-07

Justification of the ranges of $\Delta 1$ and $\Delta 2$ values to cover the plausible domain of the missing values is supported by the following, using WOMAC Pain UB1. The $\Delta 1$ will assume a value ranging from 0 to 4. This UB1 of 4 for $\Delta 1$ is selected to be reasonably higher than 1 SD of the primary endpoint of the study and is used to cover wider range of imputations. For the case of the lower boundary of $\Delta 1=0$, the missing data in the placebo group are considered as MAR. For the case of upper boundary of the range of $\Delta 1=4$, the missing data in the placebo group are considered MNAR with a fixed worsening shift of 4 from the imputed values assuming MAR of all missing WOMAC data. Such a magnitude represents a reasonable upper bound for the range of deviation from MAR imputation. The boundaries of $\Delta 2$ are selected to start from $\Delta 2=\Delta 1$ to $\Delta 2=\Delta 1+LSMD$. With the starting values of $\Delta 2=\Delta 1$, MNAR data for discontinued subjects either from the active treatment group or the placebo group are worsened by the same shift from their imputed WOMAC total score based on MAR. With the upper boundary of $\Delta 2$ defined by $\Delta 2=\Delta 1+LSMD$, the MNAR data for discontinued subjects from the active treatment group will have their WOMAC imputed scores based on MAR worsened by larger amounts that are equal to the whole LSMD rather than a fraction of the LSMD (in addition to the $\Delta 1$).

b. Multiple Imputation: Copy Reference (Placebo) Approach

Step 0: Missing data in the placebo group are imputed using a multiple imputation technique assuming MAR.

Step 1: Missing data in the active treatment group are imputed based on the conditional distribution estimated from the placebo group using a multiple imputation technique.

Step 2: A range of common shifts ($\Delta=0, 1.3333, 2.6667, 4$ units – WOMAC Pain) are added to the imputed data in Step 0 for the placebo group and in Step 1 for the active treatment group to worsen imputed scores. ($\Delta=0, 4, 8, 12$ units – WOMAC Physical Functioning) ($\Delta=0, 0.6667, 1.3333, 2$ units – WOMAC Stiffness)

Step 3: The primary MMRM model is then applied to each of the complete datasets created from Step 0 through Step 2.

Step 4: Step 0 through Step 3 are repeated $m=100$ times and PROC MIANALYZE is then applied to combine the estimates using Rubin's combination rules.

Noven Pharmaceuticals, Inc.

Protocol HP-5000-US-07

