16.1.5 SENSITIVITY ANALYSIS OF PRIMARY EFFICACY VARIABLE

Further details of sensitivity analyses are provided in [Appendix 3](#).

Sensitivity analyses will be performed to assess the impact of assumptions about missing data patterns on the primary and key secondary efficacy inferences. Additional analysis due to intercurrent events occurring in the trial will be performed.

The intercurrent events are defined as:

1. Discontinuation due to reasons related to study treatment (e.g. AE, LOE, lack of compliance, deviation from protocol, etc.),
2. Rescue medication drug use within 24 hours of WOMAC pain assessment,

Noven Pharmaceuticals, Inc.

Protocol HP-5000-US-07

3. Removal/detachment of the patch for more than 24 hours before WOMAC pain assessment.

Table B provides details on how these intercurrent events will be used for the sensitivity analyses.

Table B: Sensitivity Analysis Methods for Intercurrent Events

Analysis	Endpoint	Methods for Intercurrent Events		
		Discontinuation related to Study Medication	Rescue Medication	Patch Removal/ Detachment
Primary Efficacy	Mean change in WOMAC pain score from baseline to Week 12	1. Pattern Mixture Model	1. Pattern Mixture Model	1. Pattern Mixture Model
		2. Copy Reference Model	2. Copy Reference Model	2. Copy Reference Model

Pattern-Mixture Model and Copy Reference Sensitivity Analyses of MMRM Approach:

Robustness of the primary results under MNAR (Missing not at random) mechanisms will be assessed using pattern-mixture model and copy reference imputation approaches. All sensitivity analyses will be based on the pattern mixture model using multiple imputation for the dropout reasons and their assumed pattern of missing data as follows:

- LOE as MNAR with other missing data as MAR
- LOE and AE as MNAR with other missing data as MAR
- Any reason (all dropout) as MNAR

a. Multiple Imputation: Pattern Mixture Model (PMM)

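### SAP Appendix 3 applies the MNAR shift without regard to dropout reason, which contradicts the three reason-based patterns in SAP Section 16.1.5

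*SAP*

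**What the plan says.** SAP Section 16.1.5 bases both sensitivity methods on three patterns: "LOE as MNAR with other missing data as MAR"; "LOE and AE as MNAR with other missing data as MAR"; and "Any reason (all dropout) as MNAR". For the mechanics it says "Further details of sensitivity analyses are provided in" Appendix 3.

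The numbered steps of Appendix 3 read as follows.

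- **Pattern mixture, Step 0:** "Missing data will be imputed using a multiple imputation technique assuming MAR for all treatment groups".
- **Pattern mixture, Step 1:** the placebo shift "will be added to all imputed data in Step 0 in the Placebo group to worsen imputed scores".
- **Pattern mixture, Step 2:** the active-arm shift "is also added to the imputed data in Step 0 in the active treatment group to worsen their imputed scores".
- **Copy reference, Step 1:** missing active-arm data are imputed from the conditional distribution estimated in placebo.
- **Copy reference, Step 2:** the common shifts "are added to the imputed data in Step 0 for the placebo group and in Step 1 for the active treatment group".

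No step mentions the reason for dropout. Yet the opening of Appendix 3 lists dropout reason among the items to be tabulated, and its justification paragraph speaks of shifting the MNAR data of discontinued subjects.

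**The concern.** The first two patterns require some imputed values to stay at MAR. Step 1 says the opposite for placebo, and the other steps say nothing that would keep any value at MAR. A programmer who follows the steps would produce three blocks of identical numbers under different labels. A second programmer who follows Section 16.1.5 would produce three different blocks. Both could claim to have followed the SAP.

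At stake is how the robustness tables for the primary and key secondary endpoints are read. They are meant to show how far the conclusion depends on assumptions about LOE and AE dropouts in particular.

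**Working it through.** **1. The plan's own count.** Appendix 3 gives four values of k1 (0, 0.33, 0.67, 1) and six of k2 (0, 0.2, 0.4, 0.6, 0.8, 1). 4 x 6 = 24, as stated. Copy reference uses four shifts for pain (0, 1.3333, 2.6667, 4).

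**2. Results under each reading, WOMAC pain.**

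| | Steps read literally | Shift tied to pattern |
|---|---|---|
| Pattern mixture | 24, repeated three times | 3 x 24 = 72 |
| Copy reference | 4, repeated three times | 3 x 4 = 12 |

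In the pattern-mixture analysis the zero-shift cell is the same for all patterns under either reading. In copy reference the patterns differ even at zero shift, provided the placebo-based imputation is itself restricted by reason.

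**3. Effect on the Week 12 difference.** Let pA and pP be the shares of the active and placebo arms whose Week 12 value is shifted. The difference (active minus placebo, higher score worse) changes by

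pA x Δ2 - pP x Δ1.

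The documents do not give dropout by reason, so the rates below are assumptions (LOE / AE / other):

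- low: placebo 3/2/5%, active 2/3/5%;
- mid: placebo 8/3/7%, active 4/6/7%;
- high: placebo 12/4/12%, active 6/10/12%.

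Δ1 = 4 is the top of the plan's range. Δ2 = 5 takes k2 = 1 and an assumed LS mean difference of 1 point in size, entered so that it worsens the active arm, as the appendix intends.

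Mid case:

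- LOE: 0.04 x 5 - 0.08 x 4 = -0.12
- LOE and AE: 0.10 x 5 - 0.11 x 4 = +0.06
- any reason: 0.17 x 5 - 0.18 x 4 = +0.13

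| | LOE | LOE and AE | Any reason | Literal, all three rows |
|---|---|---|---|---|
| low | -0.02 | +0.05 | +0.10 | +0.10 |
| mid | -0.12 | +0.06 | +0.13 | +0.13 |
| high | -0.18 | +0.16 | +0.28 | +0.28 |

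The error in a row is qA x Δ2 - qP x Δ1, where qA and qP are the shares that should have stayed at MAR. For LOE in the mid case this is 0.13 x 5 - 0.10 x 4 = +0.25, which is 0.13 - (-0.12). With shifts of 4 and 5 the error is unfavourable to HP-5000 when qA/qP exceeds 4/5 = 0.8 and favourable below that.

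**4. Check by simulation.** One simulated dataset used the mid rates, 250 subjects per arm, 100 imputations, Rubin's rules and a baseline-adjusted Week 12 model in place of the MMRM. All missing values in it were dropouts. With no shift the difference was -0.694 (SE 0.306). At Δ1 = 4 and Δ2 = 5 the literal steps gave -0.387 (0.351) for every pattern. The reason-specific steps gave -0.810 (0.323), -0.478 (0.338) and -0.387 (0.351). The movements differ from the table because the dropout drawn in this dataset differs from the assumed rates, but the structure is the same.

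**The case against.** The strongest reply is that the documents should be read together. Section 16.1.5 sets the patterns and refers to the appendix only for detail. The appendix tabulates by dropout reason and describes the shift as acting on MNAR data of discontinued subjects. Only Step 1 uses the word all. On that view the steps are simply run once per pattern, and nothing collapses.

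This shows that the patterns are intended, and that much stands. A reader might infer that the sponsor has replaced three analyses with one; the documents do not support that. But the reply does not supply the missing rule. Reporting by reason does not say which values a reason selects, and the justification paragraph also calls the missing placebo data MNAR without naming a reason. The protocol (Section 13.4.3.1) promises programming detail and SAS code in the SAP, but the code visible in Appendix 2 covers only PROC MIXED and PROC LOGISTIC. The table shells mentioned in SAP Section 8 are not in the public documents.

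Two further inferences go too far.

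- **That the literal rows would all equal the any-reason analysis.** The literal steps also shift values missing for other causes: scores excluded for rescue use or patch detachment (Section 16.1.4), scores lost to a missing item (Section 7.3), and missed visits. They are broader than all dropout whenever such values exist.
- **That the literal steps multiply the intended stress by a fixed factor.** A fixed ratio needs equal dropout in both arms and an assumed LOE share. With unequal dropout even the sign can differ, as the table shows.

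It is also fair to say that these are sensitivity analyses with nominal p-values.

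**Conclusion.** The contradiction is real. Section 16.1.5 requires some imputed values to stay at MAR in two of its three patterns. Appendix 3 states an implementation rule that shifts all of them in placebo and sets no condition elsewhere. Identical rows are the consequence of coding the steps literally, not the plan's stated intent.

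That the rows coincide follows from the text alone. The numerical movements rest on assumed dropout rates and an assumed 1-point LS mean difference, and only their range is informative. The primary MMRM and the fixed-sequence test do not depend on this. The point should be settled before the sensitivity analyses are programmed, because a mislabelled LOE row could make the result look either more or less robust than it is.

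**What to change.** Amend Appendix 3 as follows.

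1. State that the steps are run once for each pattern.
2. In pattern-mixture Steps 1 and 2, add the shift only to imputed values that are missing after dropout for a reason that is MNAR in that pattern. Leave all other imputed values at MAR.
3. In copy-reference Steps 1 and 2, restrict both the placebo-based imputation and the shift in the same way. Changing Step 2 alone is not enough: active-arm subjects who dropped out for other reasons would still be imputed from placebo, and the patterns would still coincide at zero shift.
4. State separately how values missing because of rescue use, patch detachment or a missed visit are handled. Table B in Section 16.1.5 assigns both methods to rescue and detachment, while the text below it limits the MNAR imputation to data missing through early discontinuation. A blanket rule that only post-discontinuation values are shifted would contradict Table B, so the two need to be reconciled.
5. Reconcile the pattern list with the protocol. The amended text of protocol Section 13.4.3.1 treats study-treatment-related reasons as MNAR and unrelated or uncertain reasons as MAR, while SAP Section 3.3 declares no change from the protocol. Protocol Section 8.2.3 also lists adverse events under both related and unrelated reasons, so the AE pattern should say which it means. The selection rule is needed whichever list is kept.

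The cost is a few sentences in Appendix 3 and a decision on items 4 and 5. Protocol Section 8.2.3 already requires the discontinuation reason to be recorded, so no new data are needed.
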